### c. Hypothesis Testing

*H1: Individuals receiving daily BWL treatment will report significant reductions in fatigue from baseline compared to those receiving DRL.* The primary outcome measure, GFI, will be the dependent variable in the multi-level regression. We will enter time into the model first and examine fit. We will add any demographic or study measures identified as potential confounders in the preliminary analyses, and examine improvement of fit. Finally, we will add the treatment effect to the model and examine differences in fit to determine the presence and strength of the treatment effect over time. The same analyses will be conducted using our secondary fatigue outcome measure, the TBI-QOL Fatigue.

	Protocol Name:	Management of post-TBI fatigue with light exposure
	Principal Investigator:	[name]., ABPP/Cn
	Primary Contact Name/Contact Info:	[name], [contact] , [name]
	Date Revised:	3/9/16
	Study Number:	IF1556212

*H2: Individuals receiving daily BWL treatment will report significant reductions in daytime sleepiness and depressed mood as well as improvements in sleep quality and circadian rhythms from baseline compared to those receiving DRL.* Testing of this hypothesis will be identical to that for H1, with ESS (sleepiness), Neuro-QOL Depression (mood), NeuroQol Sleep (sleep quality) and circadian rhythm measures (from Actigraphy) as the dependent variables.

*H3: Treatment effects will be maintained one month after treatment completion.* Pilot data suggests that the positive effects of BWL persist beyond termination of active treatment. To address whether treatment effects are indeed maintained one month after treatment completion, we will extend the multilevel analysis for H1 to include data from the T3 follow-up assessment. One advantage of a third assessment is that the possibility of time as a non-linear effect can be explored. Model fit for a linear versus non-linear time effect will be compared to determine best fit. As in H1, any demographic or study measures identified in the preliminary analyses will be added, with examination of improvement of fit. Finally, we will add the treatment effect to the model to examine the persistence of the treatment effect over time.

d. Research Questions

*RQ1: We will assess whether treatment with BWL is associated with changes in circadian rhythms and improvements in anxiety, cognition and life satisfaction using the analyses described for H1, with Neuro-QOL Anxiety, CNS Vital Signs Neurocognitive Index and CFQ (cognition), and SWLS (life satisfaction) as the respective dependent variables.*

*RQ2: As it is not clear whether BWL's effects on PTBIF are direct effects or secondary to changes in other domains, we will examine whether PTBIF scores are mediated or moderated by mood, sleepiness, sleep quality and circadian rhythms. These analyses will focus on the magnitude of the effect, as recommended by Kraemer et al. We will use a fixed-effects approach in which the dependent variable is the GFI pre-post change. We will compare the between treatment group effect sizes for those with and without the respective potential mediator or moderator. An effect will be considered present if a substantial difference in effect size is observed. Results from these exploratory analyses could be used to guide the design of future RCTs that would focus on those subjects most likely to respond to BWL.*

*RQ3: Because current research suggests that age, gender and injury severity may be associated with treatment outcome, we will examine these individual characteristics and any others that the literature suggests may be relevant at the time of analysis. We will add these variables to the multilevel model one at a time and test to determine if the variable improves fit. Continuous variables that improve the fit will be examined further by determining the correlation between them and GFI separately for the two treatment groups, and comparing the strength of the correlations.*

e. Statistical Power

[The sample size for this study will provide adequate power to test the primary hypothesis. We will recruit enough subjects to fill the Treatment (DRL-BWL)-by-Time (pre-post) repeated measures design (40 subjects per treatment group, total N = 80). This design achieves 90% power to test the treatment effect using a Geisser-Greenhouse Corrected F Test with a 5% significance level, based on an effect size of 0.37, and achieves 81% power to test the Treatment-by-Time interaction using a Geisser-Greenhouse

	Protocol Name:	Management of post-TBI fatigue with light exposure
	Principal Investigator:	[name]., ABPP/Cn
	Primary Contact Name/Contact Info:	[name], [contact] , [name]
	Date Revised:	3/9/16
	Study Number:	IF1556212

Corrected F Test with a 5% significance level, based on an effect size of 0.32. Effect sizes (Appendix VI) were chosen based on the pilot findings, and then reduced by 20% to correct for possible inflation given the small sample size. []

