### b. Data Analyses: Overview

We will calculate descriptive statistics for all measures. We will examine distributions and address substantial non-normality using data transformations, as necessary. If we detect a significant baseline group imbalance on a demographic or clinical variable, we will include that variable as a covariate in subsequent analyses. Dropouts and treatment completers will be compared on baseline variables. We will examine associations among demographic characteristics and outcome measures to identify necessary covariates for subsequent analyses.

We will fit random effects models to test the primary hypotheses, examining the effects of treatment over time. This model is a preferable alternative to traditional repeated measures ANOVA or ANCOVA, in that it takes into account the correlated nature of repeated measurement within an individual. The model allows us to examine the influence of demographic and injury characteristics prior to the inclusion of the treatment effect. We will conduct analyses on the full Intent-To-Treat sample (all subjects randomized) using full maximum likelihood estimation. We will determine model fit using Akaike's Information Criteria.

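### The H1 step judges the BWL effect on GFI by change in model fit, with AIC the only criterion named and no test, significance level or deciding term tied to it

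*Combined protocol and SAP*

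**What the plan says.** Section 6.b: "We will fit random effects models to test the primary hypotheses", by full maximum likelihood on everyone randomised. The only fit criterion is given in the sentence that begins "We will determine model fit using Akaike". No AIC margin is given.

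Section 6.c, H1 (dependent variable GFI): time is entered first, then any confounders found in preliminary analyses. Treatment is added last, and the analyst is to "examine differences in fit to determine the presence and strength of the treatment effect over time". The same procedure serves TBI-QOL Fatigue, the H2 outcomes as numbered in Section 6.c (sleepiness, mood, sleep quality, circadian rhythms) and RQ1 in Section 6.d. For H3 as numbered there, "we will extend the multilevel analysis for H1 to include data from the T3 follow-up assessment", so H1 itself uses T1 and T2.

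Section 6.e says that the sample gives "adequate power to test the primary hypothesis". The design "achieves 90% power to test the treatment effect using a Geisser-Greenhouse Corrected F Test with a 5% significance level", with an effect size of 0.37. It also "achieves 81% power to test the Treatment-by-Time interaction", again by a Geisser-Greenhouse "Corrected F Test with a 5% significance level, based on an effect size of 0.32".

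**The concern.** The H1 sentence is the decision step for the primary efficacy claim, because the presence of an effect is to be read from a change in fit. The plan's only measure of fit is AIC. AIC is a model-selection criterion, and the rule that the lower AIC wins is not a 5% test.

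The 5% level in Section 6.e does not close the gap. It belongs to a repeated-measures F test, whereas Section 6.b prefers the random effects model to repeated-measures ANOVA. It is also applied to two terms, the treatment effect and Treatment-by-Time, without saying which decides H1.

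Two analysts could therefore follow the plan in good faith and reach different conclusions on GFI. One of them could report an effect whose 95% CI includes zero. The outcomes that borrow the H1 procedure inherit the same gap.

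**Working it through.** **Inputs.** From Section 6.e: 40 per arm, N = 80, pre-post design, 5% level, effect sizes 0.37 and 0.32, stated power 90% and 81%. From the section on number of subjects: 95 enrolled. From Section 6.b: full maximum likelihood and AIC. Assumptions: complete data, normal errors, effect size read as Cohen's f.

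**1. The plan's own power.** Noncentral F with 1 and 78 df, noncentrality N × f².
- f = 0.37: 80 × 0.37² = 10.95; power at 5% is 90.5% (stated 90%).
- f = 0.32: 80 × 0.32² = 8.19; power at 5% is 80.7% (stated 81%).

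Both reproduce, so the power figures are not in error. Under a one-parameter lower-AIC rule the same inputs give 97.1% and 92.7%. The stated power therefore describes a 5% test.

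**2. What a fall in AIC means.** For nested models differing by k parameters, AIC falls when the likelihood-ratio statistic LR exceeds 2k. Asymptotically, under no effect, P(χ²₁ > 2) = 15.7% and P(χ²₂ > 4) = 13.5%.

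**3. Finite sample, one added parameter** (group difference in T1-T2 change). LR = N × ln(1 + F/(N − 2)), with F on 1 and N − 2 df. Rates under no effect at N = 80:

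| Rule | Two-sided | Favouring BWL (half) |
|---|---|---|
| AIC falls by any amount (LR > 2) | 16.4% | 8.2% |
| 5% chi-square likelihood-ratio test (LR > 3.84) | 5.4% | 2.7% |
| AIC falls by more than 2 (LR > 4) | 4.9% | 2.5% |
| Exact 5% t/F test | 5.0% | 2.5% |

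At N = 95 the first row is 16.3%.

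**4. Two added parameters** (treatment and treatment-by-time together). With unrestricted T1 and T2 means and covariance, LR = N × ln(1 + 2F/(N − 3)), with F on 2 and N − 3 df. P(LR > 4) is 14.6% at N = 80. Simulating a random-intercept model, which is closer to the plan's wording, gives 14.3%. The rate is about 14-15% either way.

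**5. Where an effect would register.**
- Lower AIC, one parameter: |t| > √[(e^(2/80) − 1) × 78] = 1.405, p = 0.164. In SDs of change this is 1.405 × √(2/40) = 0.31.
- 5% test: |t| > 1.991, and 1.991 × √(2/40) = 0.45 SD.
- A result just at the AIC threshold has a 95% CI of 0.314 ± 0.445, or −0.13 to 0.76 SD.

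**6. Other readings.** Requiring AIC to fall by more than 4 gives about 1.6% at N = 80 with one parameter. Testing both powered terms at 5% and accepting either gives about 10% (1 − 0.95² = 9.75%; 10.4% in simulation with likelihood-ratio tests). The figures in steps 3 and 4 are therefore illustrations of particular readings.

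**The case against.** The strongest reply is that a conventional 5% test is plainly meant and that nowhere does the plan say a lower AIC shows the treatment works. Section 6.b fits the models to test the primary hypotheses. H1 speaks of significant reductions. Section 6.e attaches a 5% level to power for the primary hypothesis. RQ3, which adds terms to the same multilevel model, says that improvement in fit will be tested. The deciding term is also less open than it may look, because H1 concerns reduction from baseline relative to dim red light (DRL), which points to treatment-by-time.

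Most of this stands. Together these passages make a 5% test of treatment-by-time the likelier intention. But none of them attaches a statistic, a level or a coefficient to the H1 step. RQ3 concerns patient characteristics and names no statistic either. Section 6.e leaves two terms in play under a method that the analysis section sets aside.

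A reader might infer that the trial's false-positive rate is 16%, or that it must lie between 5% and 16%. The documents support neither. The lower-AIC rule is inferred, and step 6 of the working shows plausible readings at about 1.6% and about 10%. A reader might also infer that the rule will be chosen after the data are seen. Nothing in the documents shows this; the gap only leaves it possible.

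**Conclusion.** The concern holds as an underspecified decision rule for the primary outcome, and it should be fixed before the analysis. That no test, level, margin or deciding term is tied to the H1 step can be read directly from Sections 6.b and 6.c, and confidence in this is high. The consequence is conditional. If any fall in AIC is taken as an effect, the two-sided false-positive rate is roughly three times 5% (about 16% with one added parameter, about 14-15% with two), and a result with p = 0.16 could be reported as a BWL effect on GFI. If a 5% test is what is meant, the rate is about 5% and the stated power applies.

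The rates assume no true effect, 40 per arm and complete data. They cover the last modelling step only and leave out the data-driven choice of covariates and transformations in Section 6.b.

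**What to change.** In Section 6.b, limit AIC to choosing the form of time or the covariance structure. In Section 6.c, replace the fit comparison for H1 with wording such as:

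*H1 is decided by the T1-T2 treatment-by-time coefficient (BWL minus DRL difference in GFI change) from the multilevel model. It is tested two-sided at 5% by a t/F test with small-sample degrees of freedom (for example Kenward-Roger with REML). The estimate and 95% CI are reported.*

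T1-T2 fits the plan, because T3 enters only when the H1 model is extended for H3. Naming the t/F test matters because a chi-square likelihood-ratio test runs at 5.4% here. If REML is used for this test, Section 6.b should say so beside its full maximum likelihood statement. Apply the same rule to TBI-QOL Fatigue and the Section 6.c H2 outcomes. In Section 6.e, state that the 81% interaction power is the figure that applies to H1.

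The cost is wording only, with no extra participants or data. Relative to a lower-AIC rule, observed differences of about 0.31 to 0.45 SD of change would no longer be claimed. The less favourable of the two stated powers, 81% instead of 90%, becomes the one that applies.

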## 1) Objectives

- Aim 1: Evaluate the efficacy of 4 weeks of daily BWL exposure in reducing PTBIF immediately post-treatment and at one-month follow-up.
  - H1: Individuals receiving 4 weeks of daily BWL treatment will report significant reductions in fatigue compared to those receiving DRL
  - H2: Treatment effects will be maintained one month after treatment completion
- Aim 2: Explore potential effects of BWL exposure on mood, sleepiness, sleep quality, circadian rhythms, anxiety, cognition and life satisfaction.
  - H3: Individuals receiving 4 weeks of daily BWL treatment will report significant reductions in daytime sleepiness and depressed mood as well as improvements in sleep quality and circadian rhythms, compared to those receiving DRL
  - RQ1: Is treatment with BWL associated with improvements in anxiety, cognition and life satisfaction?
- Aim 3: Investigate potential mechanisms for effects of BWL exposure on fatigue, including changes in mood, sleepiness, sleep quality and circadian rhythms.
  - RQ2: Are treatment-related changes in fatigue mediated or moderated by mood, sleepiness, sleep quality and circadian rhythms?
- Aim 4: Determine whether individual characteristics are associated with treatment outcomes.
  - RQ3: Are demographic or other patient characteristics associated with positive treatment outcomes?

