*Treatment effects.* Change scores were used for between-group comparisons to remove effects of any baseline differences between groups. Robust effect sizes in Cohen’s “medium” and “large” ranges were seen for BWL both between and within groups (0.32-1.56) on fatigue measures (see Appendix VI for all effect sizes). In most cases, effects were somewhat decreased at follow up but were generally in the medium range. This is unexpected, as past research indicates that treatment effects dissipate after treatment is discontinued. Medium or larger effect sizes were also noted for BWL on measures of daytime sleepiness, sleep quality and mood. Effect sizes for DRL were generally small.

Actigraphy findings indicated improvements in sleep in both groups but with larger effect sizes for BWL. Circadian rhythm data were more ambiguous, with modest changes in phase and rhythmicity in both groups. These findings suggest that BWL and DRL therapy are safe, feasible and credible for use with individuals with TBI, that the measures selected were sensitive to treatment effects and that BWL may be a promising treatment for PTBIF, with potential benefits for daytime sleepiness, mood, circadian rhythms and sleep as well. Indeed, daytime sleepiness, mood, circadian rhythms, and sleep quality may actually function as mediators or moderators of BWL treatment effects on PTBIF, given their documented responsiveness to light exposure. Because of the promising initial findings in our small pilot study and the need for empirically validated PTBIF treatment, an *Intervention Efficacy* trial investigating the effect of BWL on PTBIF is warranted. Based on: 1] the literature on alerting effects and cognitive benefits of BWL and the connection between PTBIF and cognition; 2] our own unpublished research suggesting the important role of anxiety in PTBIF and sleep disturbance; and 3] potential improvements in life satisfaction resulting from BWL effects on function, we will evaluate cognition, anxiety and life satisfaction as potential secondary effects of treatment.

To date, no trials of BWL treatment have been conducted in individuals with TBI. However,

	Protocol Name:	Management of post-TBI fatigue with light exposure
	Principal Investigator:	[name]., ABPP/Cn
	Primary Contact Name/Contact Info:	[name], [contact] , [name]
	Date Revised:	3/9/2016
	Study Number:	IF1813452

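### The analysis of one-month maintenance names no BWL-DRL comparison at T3, so an effect present only at T2 could be read as persistence

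*Combined protocol and SAP*

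**What the plan says.** Aim 1 in the Objectives covers fatigue at the end of treatment and at one-month follow-up, and gives the second its own hypothesis: "H2: Treatment effects will be maintained one month after treatment completion". The analysis section numbers this hypothesis H3.

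Its analysis is described in section 6.c (Hypothesis Testing). The steps are:

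- "we will extend the multilevel analysis for H1 to include data from the T3 follow-up assessment";
- "Model fit for a linear versus non-linear time effect will be compared to determine best fit";
- covariates are added, again with a look at fit;
- finally, "we will add the treatment effect to the model to examine the persistence of the treatment effect over time".

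The H1 analysis that this extends adds a treatment term in the same way, to "examine differences in fit to determine the presence and strength of the treatment effect over time". Section 6.b gives the criterion: "We will determine model fit using Akaike's Information Criteria".

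Section 6.e (Statistical Power) does separate a treatment effect from a treatment-by-time interaction, but only for a pre-post design without T3.

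**The concern.** The term that is meant to answer the maintenance question is not defined. It could be a group main effect averaged over three visits, a difference in linear slope, a difference in a non-linear time profile, or a combination. Most of these do not isolate T3. A main effect averages T2 with T3. A joint test over three visits asks whether the arms differ anywhere in their profiles, and a difference at T2 alone is enough to make it positive.

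The plan's own Background leaves the answer open. It says that "past research indicates that treatment effects dissipate after treatment is discontinued", but of the pilot it reports: "In most cases, effects were somewhat decreased at follow up but were generally in the medium range". Full loss, partial loss and full retention are all plausible, so the analysis has to tell them apart. At stake is the one-month half of Aim 1. The T2 result and the sample size are not affected.

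**Working it through.** **Inputs.** From section 6.e: 40 per arm, 5% significance, interaction effect size f = 0.32 with 81% power, treatment effect size f = 0.37 with 90% power. From Study Timelines: T2 after 4 weeks of treatment and T3 4 weeks later, so visits are about equally spaced. Assumed, because the document gives no values: compound symmetry with between-visit correlation ρ = 0.3, 0.5 or 0.7, and T3 data on all 40 per arm.

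**The plan's own figures.** Non-central F on 1 and 78 df, with λ = N·f²:

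- f = 0.32: λ = 80 × 0.1024 = 8.19, power 0.807 (stated 81%).
- f = 0.37: λ = 80 × 0.1369 = 10.95, power 0.905 (stated 90%).

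Both reproduce. With two groups, f = 0.32 corresponds to d = 2f = 0.64 SD of the change score.

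**Set-up.** In single-visit SD units the T2 difference is δ = 0.64·√(2(1−ρ)), which is 0.757, 0.640 and 0.496 for the three correlations. The arm differences at T1, T2 and T3 are (0, δ, gδ), where g is the share of benefit kept at T3. Their covariance is (2/40)R, with R compound symmetric.

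**Non-centralities** (note that δ²/(1−ρ) = 0.8192):

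- Main effect, 1 df: 20·δ²(1+g)² / [3(1+2ρ)]. At g = 0 this is 2.39, 1.37 and 0.68.
- Linear slope given a main effect, 1 df: 20·(gδ)² / [2(1−ρ)] = 8.19·g². At g = 0 this is 0.
- Non-linear (saturated) interaction given a main effect, 2 df: 20·S/(1−ρ), where S is the sum of squared deviations of the three differences from their mean. S is 2δ²/3, δ²/2 and 2δ²/3 at g = 0, 0.5 and 1, giving 10.92, 8.19 and 10.92.
- Joint tests add the relevant components.

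The 5% test compares the statistic with the chi-square critical value. AIC improves when the statistic exceeds twice its df.

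**All benefit lost at T3 (g = 0), chance of a positive result:**

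| Reading of the added term | 5% test, ρ = 0.3 / 0.5 / 0.7 | AIC improves |
|---|---|---|
| Linear slope beyond a main effect (1 df) | 0.05 at each | 0.16 at each |
| Linear slope, no main effect (1 df) | 0.16 / 0.09 / 0.06 | 0.34 / 0.23 / 0.18 |
| Main effect + linear interaction (2 df) | 0.263 / 0.166 / 0.105 | 0.44 / 0.32 / 0.23 |
| Main effect only (1 df) | 0.340 / 0.215 / 0.131 | 0.554 / 0.408 / 0.291 |
| Non-linear interaction (2 df) | 0.85 at each | 0.93 at each |
| Main effect + non-linear interaction (3 df) | 0.879 / 0.850 / 0.827 | 0.938 / 0.920 / 0.905 |

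A 20,000-run simulation agrees for the main effect (0.34 / 0.21 / 0.13) and the 2-df interaction (0.84 to 0.85), and puts the T1-to-T3 contrast at 0.05.

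**Does the 2-df interaction track maintenance?** It is positive in 85%, 73% and 85% of trials when none, half or all of the benefit is kept. It does not. When half is kept there is a real T3 benefit, so a positive there is wrong only as a claim of full maintenance.

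**Which time shape would be chosen?** A maximum-likelihood random-intercept simulation (flat DRL arm, 1,500 trials per cell) has AIC choosing non-linear time in 96–97%, 84% and 57–60% of trials at g = 0, 0.5 and 1. With treatment crossed with the chosen shape and judged by AIC, the result is positive in 88–93%, 82–92% and 95–99%.

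**A named T1-to-T3 contrast.** This is positive in 5% at g = 0. Power in favour of BWL is about 0.30 at g = 0.5 and 0.81 at g = 1 (simulated, 40,000 trials per cell). If tested only after a significant T2 contrast, it is 0.28 and 0.70.

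**Precision of T3 minus T2.** δ divided by its standard error is 0.64·√20 = 2.862, so the 95% CI half-width is 1.99/2.862 = 0.70 of the planned T2 effect.

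**The case against.** The strongest reply is that this is under-specification and not a test that gives a wrong answer. The rule of reading an effect from differences in fit is stated for H1. The maintenance paragraph says only that persistence will be examined. When the benefit exists only at T2, a treatment-by-time test ought to reject, because the profiles do differ. It becomes an error only if someone then reports maintenance without looking at T3. A treatment-by-non-linear-time model with three visits contains the T3 difference, so a sensible analyst would see it. That all stands, and the large percentages are conditional on an omnibus or fit-based reading. But nothing in the plan says that the T3 estimate will be tested or will decide the hypothesis.

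A second reply is that one permitted reading is already safe. With equally spaced visits, complete data and compound symmetry, the linear slope beyond a main effect is the T1-to-T3 contrast. That is correct. However, time shape is to be chosen by fit, and in the simulation the linear shape is seldom chosen when the benefit is lost.

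Third, the main-effect-only reading sits poorly with the plan's references to effects over time. It is the less natural reading, but it is not excluded.

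Fourth, a significant T1-to-T3 contrast shows benefit at one month, not full maintenance. This also stands and limits what may be claimed.

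**Conclusion.** The concern holds. The maintenance hypothesis has no defined T3 comparison, and readings that the wording permits give a positive result in 5% to 88% of trials by a 5% test, or 16% to 94% by AIC, when nothing remains at T3. These figures rest on the planned T2 effect, 40 per arm with T3 data, compound symmetry with correlation 0.3 to 0.7, and complete loss of benefit, which is the unfavourable case. Random slopes were not examined. Misreading T2-only benefit as persistence further requires that H1's fit rule, or an overall test, be taken as the answer; the plan neither says this nor rules it out. The plan should be changed on this point, but neither the T2 analysis nor the sample size depends on it.

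**What to change.** In section 6.c, replace the fit-based step for this hypothesis with the following:

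- Fit visit as a categorical factor (T1, T2, T3) with treatment-by-visit terms.
- Name the BWL-DRL difference in GFI change from T1 to T3, two-sided 5% with 95% CI, as the test of one-month benefit.
- Report it beside the T2 estimate and the T3-minus-T2 difference between arms, each with its 95% CI.
- State that overall improvement in fit will not be used to claim maintenance.

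Optionally, test T3 only after a significant T2 contrast. That requires H1 to be worded as a T2 contrast too.

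The cost is SAP wording; no new data or participants are needed. Power is about 81% if the benefit is fully kept and 30% if half is kept, or about 70% and 28% with the gate. Because the T3-minus-T2 interval is about ±70% of the planned T2 effect, a significant T3 contrast supports a claim that benefit is still present at one month, not that it is fully maintained. The plan should say so.

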**b) Study Timelines**

Subjects' participation in the study will last approximately two months. Assessments will be conducted at three points: T1 (baseline), T2 (end-of-treatment) and T3 (follow-up at one month post treatment). Actigraph data will be collected for 3 days at T1 (prior to the initiation of treatment). Participants will use the light box for 4 weeks and then return at T2 for repeat administration of the measures and Actigraphy for 3 more days. T3 will take place 4 weeks after light box treatment is completed and will not involve the Actigraph.

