After one month of light treatment (T2), we will re-administer the baseline battery along with satisfaction and user experience questionnaires and 3 more days of Actigraphy. One month after T2, we will administer the assessment battery a third and final time (T3). Research team members who conduct outcome assessments will be blind to participants' treatment allocations. They will enter the data only after the participants have completed all study assessments (i.e. after T3) to avoid bias. Participants will be asked not to reveal treatment allocation to research team members. Participants will also be asked to refrain from light treatment in the month intervening between T2 and T3. Upon completion of follow-up, interested participants will be offered a discount coupon to purchase their own light box if they wish to do so.

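### RQ2's with/without comparison of arm effects does not measure mediation

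*Combined protocol and SAP*

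**What the plan says.** Aim 3 in Section 1 poses the question: "Are treatment-related changes in fatigue mediated or moderated by mood, sleepiness, sleep quality and circadian rhythms". Section 6.d repeats it. It says that it is unclear whether BWL's "effects on PTBIF are direct effects or secondary to changes in other domains", and takes the GFI pre-post change as the dependent variable. The method is then one sentence, "We will compare the between treatment group effect sizes for those with and without the respective potential mediator or moderator", and the decision rule another: "An effect will be considered present if a substantial difference in effect size is observed".

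Section 6.d does not say how a participant is classed as with or without a variable, whether that refers to baseline status or to change on treatment, where a continuous scale is cut, or how large a substantial difference is. It specifies no interval, no mediator-adjusted arm effect and no indirect effect.

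H2 as numbered in Section 6.c (H3 in Section 1) tests the effect of treatment on the same four domains. No step then estimates the path from those domains to GFI. RQ2 is labelled exploratory. A methods paper is cited for the focus on magnitude, but it is not among the documents, so this point judges the rule as written.

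**The concern.** Whether an effect is direct or passes through another domain is a mediation question about variables that treatment itself changes. A difference between two stratum-specific arm effects is a measure of effect modification. If strata are formed on a variable that carries the treatment effect, both stratum effects fall below the overall effect. That fall carries the information on mediation, and the written rule does not use it. It looks only at whether the two strata differ from each other.

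The rule could therefore miss a domain that carries the whole benefit. It could also report a domain that only modifies the effect, with nothing to show which of the two had been found. What is at stake is the answer to Aim 3 on mechanism. H1 and the sample size are not affected.

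**Working it through.** **Inputs from the plan (Section 6.e).** 40 per arm, N = 80, 5% level, effect sizes 0.37 (treatment) and 0.32 (treatment by time). Reading these as Cohen's f, a noncentral F(1, 78) with λ = 80f² gives power 0.905 and 0.807, which matches the stated 90% and 81%. Read as Cohen's d, they give only 0.38 and 0.30. So 0.32 is taken as f, and d = 2 × 0.32 = 0.64. The plan gives no figure for RQ2 itself.

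**Assumptions (not in the documents).** Mediator change M = 0.8T + e and GFI change Y = direct·T + b·M + error, scaled so that a positive effect is benefit. Both have within-arm SD 1. There is no treatment-by-mediator interaction, and direct + 0.8b = 0.64. The mediated share is 0, 0.5 or 1, so b = 0, 0.4 or 0.8.

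**Normal mediator, median cut.** Centre the arm means at +0.4 and −0.4 and cut at 0. With φ(0.4) = 0.3683 and Φ(0.4) = 0.6554:

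- Above the cut, the mean of M is 0.4 + 0.3683/0.6554 = 0.962 on BWL and −0.4 + 0.3683/0.3446 = 0.669 on dim red light (DRL). The difference is 0.293.
- Below the cut, the means are −0.669 and −0.962. The difference is again 0.293.
- The pooled within-stratum variance of M is 0.399 in both strata.
- Half mediated: (0.32 + 0.4 × 0.293)/√(0.16 × 0.399 + 0.84) = 0.437/0.951 = 0.46 in each stratum.
- Fully mediated: (0.8 × 0.293)/√(0.64 × 0.399 + 0.36) = 0.235/0.785 = 0.30 in each stratum.

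The equality comes from symmetry, not from the chosen shift. With a shift of 1.0 SD the stratum effects are 0.45/0.45 (half) and 0.27/0.27 (full).

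**Other mediators and cuts (high-minus-low difference in d).**

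| Mediator and cut | None | Half | Full |
|---|---|---|---|
| Normal, median | 0.00 | 0.00 | 0.00 |
| Binary (31% vs 69%) | 0.00 | 0.00 | 0.00 |
| Normal, 30th percentile | 0.00 | +0.08 | +0.16 |
| Normal, 70th percentile | 0.00 | −0.07 | −0.16 |
| Exponential, right skew, median | 0.00 | −0.24 | −0.62 |
| Exponential, left skew, median | 0.00 | +0.24 | +0.63 |

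At the 20th and 80th percentiles, full mediation gives +0.25 and −0.25. For the binary mediator, the effect in each stratum falls from 0.64 to about 0.35 to 0.00, yet the difference stays at zero.

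**A pure moderator.** Take a baseline variable that treatment does not shift, with a slope difference of 0.4. Its mean above or below the median is ±0.798, so the arm effects are 0.64 ± 0.4 × 0.798, or about 0.95 and 0.32 once standardised. The difference is +0.63, the same as for the left-skewed full mediator.

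**Noise at 40 per arm.** With a median cut, the cells hold about 40 × 0.655 = 26.2 and 13.8 people. The variance of the contrast is about 2 × (1/26.2 + 1/13.8) = 0.221, an SE of 0.47. If substantial meant 0.5 (an assumption), the contrast would pass in about P(|Z| > 0.5/0.47) = 29% of trials. Simulation of the symmetric case gives 31–32% with no mediation and 29% with full mediation. At d = 0.32 and shift 0.5 it gives 29% for both.

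**The case against.** The strongest objections, and what remains of each:

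- **RQ2 is exploratory, and the use it names is not the faulted half.** The plan says the results could help future trials focus on likely responders. That is a moderator question, and for a baseline moderator the contrast is valid in form. This stands and limits the consequence to the mechanism reading of Aim 3. Exploratory status excuses imprecision, but not a statistic that does not address the question.
- **The with/without wording may refer to baseline status.** The documents do not say. On that reading the contrast addresses moderation only, and the mediation half of RQ2 has no analysis at all.
- **Flagging a true modifier is a correct answer to half of the question.** That is fair. It misleads only if the variable is then called a mediator, but the rule gives no way to tell which label applies.
- **The skew figures use untransformed data, and Section 6.b provides for transformation.** This stands as a limit on those two rows. A more symmetric mediator moves the contrast towards zero, so transformation does not make the rule detect mediation.
- **The 29–32% rates reflect noise at an assumed threshold.** True; they apply equally to the moderator half (29.4% flagged when no moderator exists). What matters here is that the rate hardly changes between no mediation and full mediation.
- **The replacement can mislead too.** This also stands, and its size is given with the fix.

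**Conclusion.** The concern holds. As written, RQ2's only criterion does not measure mediation. For a binary mediator, or a roughly symmetric one cut near the median, and with no treatment-by-mediator interaction, the contrast is zero at any mediated share. Outside those conditions it ranges from about −0.6 to +0.6 under full mediation in the cases examined. Its sign and size are then set by the cut and the shape of the distribution as well as by the mediated share, so it cannot be read as that share or told apart from moderation.

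The zero result is algebraic. The other magnitudes rest on the assumed total effect, mediator shift, distribution and cut, none of which the plan gives for RQ2. The fault is confined to the mediation half of an exploratory question. It should be corrected, but it does not bear on the primary conclusion.

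**What to change.** **Mediators.** Replace the with/without comparison by an estimate of the indirect effect. Estimate the effect of treatment on the T1–T2 change in the mediator, and the slope of GFI on the mediator adjusted for treatment and both baselines. Report their product with a bootstrap 95% CI.

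**Moderators.** Report the treatment-by-baseline-value interaction on GFI change with a 95% CI, keeping the variable continuous. With a true slope difference of 0.5, this detects 57.8% against 39.5% for a median split at the 5% level.

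Keep RQ2 exploratory and state three limits:

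- **Precision.** Under full mediation the median 95% CI is 0.29 to 1.01 at d = 0.64 and 0.05 to 0.63 at d = 0.32. The interval excludes zero in 5.5%, 90.6% and 94.9% of trials at shares of 0, 50 and 100% for d = 0.64, and in 3.5%, 48.3% and 64.1% for d = 0.32.
- **Common causes.** With no mediator-to-fatigue path but an unmeasured common cause, the interval excludes zero in 41.5% of trials at a within-arm correlation of 0.2 and in 90% at 0.4.
- **Direction.** Mediators and GFI are both taken at T2, when "we will re-administer the baseline battery along with satisfaction and user experience questionnaires and 3 more days of Actigraphy" applies. If fatigue change drives the mediator and no reverse path exists, the interval excludes zero in 31% of trials at a within-arm correlation of 0.5 and in 54% at 0.7 (d = 0.64). The result supports association only.

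The cost is SAP wording and modest programming on data already collected. The Section 6.c analysis of the four domains already supplies the treatment-to-mediator path.
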